### Shift in MIDAS Categories

In addition to the analyses described above, a shift analysis of the MIDAS level of disability categories from baseline to each later assessment will be presented for each treatment group. The proportion of subjects who shift from moderate or severe disability (Grade III or IV) during the run-in period to little or no disability (Grade I) and the proportion of subjects who shift from moderate or severe disability (Grade III and IV) to mild, little or no disability (Grade II and I) at each later assessment will be evaluated using a chi-square test.

### **8.4.3 Other Efficacy Analyses**

#### **8.4.3.1 Blinding Assessment**

To assess whether subjects were blind to device assignment, the Bang blinding index will be used. The number and percentage of subjects reporting each category will be reported. The Bang blinding index and the corresponding two-sided, 95% CI of the blinding index will be estimated for each treatment group as described in Appendix 2. If the two-sided, 95% confidence interval includes 0, then the null hypothesis of unsuccessful blinding will be rejected.

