### 3.5 Sample Size

Table 1 provides the required sample size per treatment group when the number of migraine days per 28-day period is used as the primary outcome measure. Sample size calculations are based on the clinically meaningful difference between active and sham treatment groups in change from baseline. Assuming a type I error of 5% (two-sided) and 90% power, Table 1 displays the required sample sizes for different values of the common standard deviation (2.0, 2.5, 3.0 and 3.5) and the presumed difference between treatment groups (1, 1.5 and 2 days). Selecting an improvement of 1 day and a common standard deviation of 2.5 requires 133 subjects per treatment group. With 15% drop-out during the randomized treatment period, a total of 160 subjects per treatment group (or 320 subjects total) would need to be randomized.

**Table 1: Required Sample Size per Treatment Group  
Assuming Type I Error ( $\alpha$ ) = 5% (two-sided) and 90% Power**

Variability (Common SD*, $\sigma$ )	Clinically Significant Improvement: Active – Sham = $\Delta$		
	1-day	1.5-day	2-day
2.0	86	--	--
2.5	133	60	34
3.0	191	86	49
3.5	259	115	66

\*Estimated standard deviation for change from baseline. Standard deviations for baseline and post treatment scores are between 2.0 to 3.5.

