### *Other Endpoints*

The study subject will complete blinding questionnaires at 1-week (V3) into the randomized period and at the completion of randomized period (V6) as part of the data collection requirements. The blinding questionnaire asks subjects which treatment they think they received (“Active Stimulation”, “Sham Control”, or “Don’t know”).

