## Appendix 2: Bang Blinding Index

To assess the blinding, the Bang blinding index and corresponding confidence interval will be estimated as follows. A 2x3 table will be constructed as shown:

Assignment	Guess			Total
	Active	Sham	Do not Know (DK)	
Active	$n_{11}(p_{1 1})$	$n_{12}(p_{2 1})$	$n_{13}(p_{3 1})$	$n_{1.}$
Sham	$n_{21}(p_{1 2})$	$n_{22}(p_{2 2})$	$n_{23}(p_{3 2})$	$n_{2.}$
Total	$n_{.1}$	$n_{.2}$	$n_{.3}$	$N$

Where  $p_{j|i} = P(\text{guess } j|\text{assignment } i)$  for  $i = 1(\text{Active}), 2(\text{Sham})$ , and  $j = 1(\text{Active}), 2(\text{Sham}), 3(\text{DK})$ , where DK denotes Don't Know. N is the total number of respondents.

If data is constructed in a 2x3 format as shown in the above table, let us define

$$r_{j|i} = p_{j|i}/(p_{1|i} + p_{2|i})$$

which is the proportion of correct guesses among participants who provided certain guesses other than DK in the  $i$ -th arm. Bang's BI is defined as  $(2 r_{j|i} - 1) * (p_{1|i} + p_{2|i})$  and can be estimated by:

$$\text{Bang's BI} = (2n_{ii}/(n_{i1} + n_{i2}) - 1) * ((n_{i1} + n_{i2})/(n_{i1} + n_{i2} + n_{i3}))$$

And its variance is given by

$$\text{Var}(\text{Bang's BI}) = (p_{1|i}(1 - p_{1|i}) + p_{2|i}(1 - p_{2|i}) + 2p_{1|i}p_{2|i})/n_i$$

Bang's BI is between -1 and +1 inclusive and can be interpreted as the proportion of participants who answered correctly on the  $i$ th arm beyond chance level.

A rule of thumb explanation on how to interpret Bang's BI is provided as follows:

- If  $r_{j|i}=1$  and  $n_{i3}=0$  (means all responses are correct), then  $\text{BI}_i=1$  (complete unblinding)
- If  $r_{j|i}=0$  and  $n_{i3}=0$  (means all responses are incorrect), then  $\text{BI}_i=-1$  (opposite guessing)
- If  $r_{j|i}=0.5$  (means 50% responses are correct), then  $\text{BI}_i=0$  (random guessing)

So, it is desired to show  $\text{BI}_i$  around 0. To test successful blinding, the null and alternative hypotheses can be constructed as follows:

$H_0$ : unsuccessful blinding vs  $H_1$ : successful blinding

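### The blinding rule reads a 95% interval that includes 0 as proof of successful blinding; without a margin it shows only that random guessing was not ruled out

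*SAP*

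**What the plan says.** SAP section 8.4.3.1 asks for the number and percentage of subjects in each guess category, and for Bang's BI with a two-sided 95% confidence interval in each arm. It then adds a decision rule: "If the two-sided, 95% confidence interval includes 0, then the null hypothesis of unsuccessful blinding will be rejected".

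Appendix 2 gives the estimator and its variance. It offers three reference points: 1 for complete unblinding, -1 for opposite guessing and 0 for random guessing. It says that values near 0 are wanted. It ends with "To test successful blinding, the null and alternative hypotheses can be constructed as follows", followed by unsuccessful blinding as the null and successful blinding as the alternative. Neither hypothesis is tied to a value or range of BI.

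Section 7.4.2 (Other Endpoints) has subjects answer Active, Sham or Don't know at V3 (week 1) and V6 (end of the randomized period). The SAP states no expected Don't-know share, and no power or error rate for the blinding test.

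**The concern.** A two-sided 95% interval that contains 0 is the non-rejection region of the test of BI = 0. The SAP treats this non-rejection as a rejection of the opposite hypothesis. Rejecting unsuccessful blinding would require the data to exclude the BI values that count as unsuccessful. The SAP never says which values those are, so no interval can do it.

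Three consequences follow.

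- The 5% error rate applies to the wrong event. It is the chance of denying success to an arm that guesses at random. The chance of declaring success when subjects do guess correctly beyond chance is uncontrolled.
- For a true BI other than 0, fewer respondents widen the interval and generally make success more likely.
- A sham arm whose interval lies wholly below 0, because sham subjects mostly guess Active, leaves unsuccessful blinding standing. Appendix 2 itself distinguishes that pattern from unblinding.

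The trial is sham-controlled and its primary endpoint comes from a subject diary. A formal statement that unsuccessful blinding was rejected would therefore be read as support for that endpoint. No analysis population, primary test or sensitivity analysis uses BI.

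**Working it through.** **Inputs.** SAP section 3.5 states that a 1-day difference with SD 2.5 "requires 133 subjects per treatment group" at 5% two-sided alpha and 90% power, and 160 per group randomized after 15% drop-out. The t-test has 89.9% power at 132 per group and 90.1% at 133, so 133 is reproduced. For drop-out, 133/0.85 = 157, close to the stated 160. These numbers serve here only to size the blinding interval. The Don't-know share is assumed: 30%, with a range of 50% to 0%.

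**Variance.** Let p1 and p2 be the shares guessing Active and Sham in an arm, and g = p1 + p2. The Appendix 2 variance simplifies:

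[p1(1 - p1) + p2(1 - p2) + 2·p1·p2]/n = [g - (p1 - p2)²]/n = (g - BI²)/n.

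**Chance that the rule declares success.** P(interval includes 0) = Φ(1.96 - BI/SE) - Φ(-1.96 - BI/SE).

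For BI = 0.20, g = 0.7 and n = 133: SE = √((0.70 - 0.04)/133) = 0.0704 and BI/SE = 2.84. The result is Φ(-0.88) less a negligible term, or 0.19.

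| True BI | n = 133: 30% Don't know (50% to 0%) | n = 160: 30% Don't know (50% to 0%) |
|---|---|---|
| 0.10 | 72% (62% to 79%) | 67% (56% to 75%) |
| 0.15 | 44% (29% to 58%) | 36% (22% to 52%) |
| 0.20 | 19% (8% to 35%) | 12% (4% to 27%) |
| 0.30 | under 1% (0% to 5%) | under 1% (0% to 2%) |

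A multinomial simulation that uses the estimated variance (400,000 draws) agrees within 0.02. At n = 133 and 30% Don't know it gives 0.711, 0.442, 0.197 and 0.009.

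**Worked example, n = 133.** Take 55 correct, 38 wrong and 40 Don't know.

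- BI = (55 - 38)/133 = 0.128.
- SE = √((93/133 - 0.128²)/133) = 0.072.
- 95% interval: -0.013 to 0.268.

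The rule declares success, although 55/93 = 59% of those who guessed were right and the interval reaches 0.27.

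**Effect of sample size.** At true BI 0.20 and 30% Don't know, the same formula gives success in 19% of cases at n = 133, 52% at n = 60 and 73% at n = 30. Two data sets show the reversal:

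- 14 correct, 8 wrong, 8 Don't know (n = 30): BI 0.20, interval -0.10 to 0.50. Declared successful.
- 560 correct, 490 wrong (n = 1,050): BI 0.07, interval 0.006 to 0.127. Not declared successful, although values above 0.13 are excluded.

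**Opposite guessing.** By symmetry, a sham arm with true BI -0.20 and n = 133 fails the rule in 1 - 0.19 = 81% of cases (93% to 65% for 50% to 0% Don't know).

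**The case against.** The strongest reply is that little depends on this. Blinding is listed under other objectives and other efficacy analyses. Section 8.4.3.1 already requires the counts and the interval, so a reader will see an upper limit of 0.27 whatever label is attached. That is a fair limit on the importance of the point. It does not make the labelled conclusion valid.

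Second, 72% at BI 0.10 is an error rate only if 0.10 is unacceptable, and clear unblinding (BI 0.30) is nearly always caught at the planned size. Both statements are true. The SAP does not say what is acceptable, however, and that is the defect. The table shows how the rule behaves and sets no threshold.

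Third, the worked example is inconclusive and does not demonstrate unblinding: 55/133 = 41% of all respondents were right, and 55 of 93 does not differ significantly from chance (exact two-sided p = 0.10). This also stands, and it supports the point, because the rule turns an inconclusive interval into a positive finding.

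Fourth, denying success to an interval wholly below 0 fits the stated wish for values near 0. Whether opposite guessing counts as failed blinding is indeed a judgement. The 81% describes what the rule does and is not a measure of harm. The SAP should make that choice openly.

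**Conclusion.** The concern holds. Section 8.4.3.1 and Appendix 2 together draw a conclusion that the interval cannot support, and nothing else in the SAP supplies a margin that would rescue it. At 133 per arm and 30% Don't know, the rule declares success in 72% of cases at true BI 0.10, 44% at 0.15 and 19% at 0.20. It seldom does so at 0.30. The exposure is therefore to modest unblinding, or to fewer respondents than planned.

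The percentages rest on the assumed Don't-know share and on 133 to 160 respondents per arm; at V3 the number may be nearer 160, where the rates are lower. The logical fault depends on neither assumption. Only the formal blinding statement is affected, not the primary result.

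**What to change.** Before unblinding, delete the rejection sentence in section 8.4.3.1 and the null and alternative hypotheses at the end of Appendix 2. Keep the planned counts and BI with its 95% interval by arm, report them descriptively at V3 and V6, and read negative values as opposite guessing, not as unblinding.

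If the sponsor wants a formal claim, pre-specify and justify a margin:

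- If only correct guessing beyond chance matters, claim success when the upper limit is below the margin.
- If opposite guessing is also to count as failure, require the whole interval to lie inside a two-sided margin.

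The descriptive version costs wording only. A formal claim becomes harder to make. With a purely illustrative margin of 0.2, true BI 0, n = 133 and the 95% interval, simulation gives about 58% success per arm for the two-sided form (81% to 27% for 50% to 0% Don't know) and about 79% for the upper-limit form (90% to 64%). The confidence level matters: with a 90% interval (two one-sided 5% tests) the two-sided form rises to about 74% (90% to 51%), and the upper-limit form to about 87% at 30% Don't know. The level should therefore be fixed together with the margin.

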**Figure 1: Diagram of Study Design**

### 3.2 Randomization

Subjects will be randomized to either the active treatment arm or sham control arm (allocation 1:1) under a randomized variable block design, stratified by study site.

Subjects will be randomized using Merge eClinical OS Interactive Web Response system (IWRS) via computer key board data entry for a web based interface.

The site personnel (the investigator or his designee) will enter the required study and subject information and will then be provided with a subject randomization number and device serial number. Once subject numbers, serial numbers, and randomization numbers have been assigned, they cannot be reassigned.

The IWRS will provide the site personnel confirmation of the randomization number and device serial number assigned to each subject.

A sponsor designee will also have a copy of the randomization schemes for each study site and will be responsible for providing the un-blinded trainer with the randomization schemes.

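### The blinding rule tests each arm's Bang index against 0 without regard to sign, so it cannot tell a lean towards 'Active' shared by both arms from real unblinding

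*SAP*

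**What the plan says.** SAP Section 7.4.2 (Other Endpoints) has subjects answer a blinding question at V3 and V6. "The blinding questionnaire asks subjects which treatment they think they received", with three possible answers: active, sham or don't know.

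Section 8.4.3.1 reports the count and percentage of each answer. It also says that the Bang index and "the corresponding two-sided, 95% CI of the blinding index will be estimated for each treatment group as described in Appendix 2". The decision rule follows: "If the two-sided, 95% confidence interval includes 0, then the null hypothesis of unsuccessful blinding will be rejected".

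Appendix 2 defines the index within one arm and says that it "can be interpreted as the proportion of participants who answered correctly on the" given arm beyond chance level. Its guide to reading the index covers three values: +1 is complete unblinding, 0 is random guessing, and -1 is opposite guessing. The last is the case where no one answers don't know and the pattern "means all responses are incorrect". Appendix 2 wants values near 0 and sets unsuccessful blinding as the null and successful blinding as the alternative.

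Neither place contrasts the two arms, says how the two arm results combine, or interprets a positive index in one arm together with a negative index in the other.

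**The concern.** Subjects are blind to assignment when what they guess does not depend on the arm they are in. That is a comparison between arms. The rule asks a different question in each arm: whether correct and incorrect guesses balance. The answer 'Active' is correct in one arm and incorrect in the other. Any general tendency to guess 'Active' therefore pushes the two indices away from 0 in opposite directions, even if no one has any information about the allocation.

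The trial is sham-controlled and its primary endpoint is counted from a subject diary, so readers will look at the blinding result when they judge the efficacy result. A pre-specified rule that cannot separate a shared response tendency from knowledge of assignment gives them a poor guide.

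**Working it through.** **Inputs from the SAP.** The estimator and variance are in Appendix 2, and the rule is in Section 8.4.3.1. Section 3.5 gives 160 randomized per arm and 15% drop-out, so 160 x 0.85 = 136 respondents per arm at the end of the randomized period. The SAP gives no numerical figure for the blinding rule itself. Its sample size, which serves here only to set the number of respondents, reproduces: 133 per arm by the noncentral t, and 133/0.85 = 157 against the stated 160.

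**Assumed.** The guess percentages, because the SAP gives none. The main range uses 35% 'Don't know' and a varying lean d = P(guess Active) - P(guess Sham).

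**Step 1: simplify the estimator.** In arm i, (2 x correct/(correct + incorrect) - 1) x (correct + incorrect)/n = (correct - incorrect)/n. So BI = P(correct) - P(incorrect).

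**Step 2: simplify the variance.** p1(1-p1) + p2(1-p2) + 2 p1 p2 = (p1 + p2) - (p1 - p2)^2. With q = 1 - P(Don't know), the variance is (q - BI^2)/n.

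**Step 3: identical guesses in both arms.** In the active arm 'Active' is correct, so BI = +d. In the sham arm 'Active' is incorrect, so BI = -d. Whether a CI includes 0 depends only on |BI| and its standard error, and both are the same for +d and -d. The pattern (+d, -d), with no information on assignment, and the pattern (+d, +d), which is unblinding, therefore meet the rule with the same probabilities.

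**Step 4: one worked case.** Take 45% Active, 20% Sham and 35% Don't know in both arms, n = 136. Then d = 0.25 and SE = sqrt((0.65 - 0.0625)/136) = 0.0657. The active arm gives 0.25 +/- 1.96 x 0.0657 = 0.121 to 0.379. The sham arm gives -0.379 to -0.121. Both exclude 0, so unsuccessful blinding is rejected in neither arm.

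**Step 5: size over a range of leans.** Simulation with identical guesses in both arms, 35% Don't know, 136 per arm, 200,000 trials per row:

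| d | At least one CI excludes 0 | Both CIs exclude 0 |
|---|---|---|
| 0 | 10% | 0.3% |
| 0.05 | 22% | 1% |
| 0.10 | 53% | 10% |
| 0.15 | 84% | 36% |
| 0.25 | over 99% | 93% |

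The number of respondents matters little: at d = 0.15 the first column is 83% with 133 per arm and 89% with 160. The expected CI starts to exclude 0 at |BI| = sqrt(1.96^2 x q/(n + 1.96^2)). That is 0.134 for this case, and about 0.11 to 0.17 for 133 to 160 per arm with 50% to 0% Don't know.

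**Step 6: the between-arm contrast.** BI_active + BI_sham is 0 whenever guesses are independent of the arm, since +d and -d cancel. Its variance is the sum of the two arm variances. Its 95% CI excludes 0 in about 5% of the trials in every row above.

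**Step 7: what the contrast misses.** Take active 55/35/10 and sham 40/20/40 (Active/Sham/Don't know). The indices are 0.55 - 0.35 = +0.20 and 0.20 - 0.40 = -0.20, and the sum is 0. Yet guesses depend on the arm: at 136 per arm the expected counts give chi-square 33.3 on 2 df, p about 6e-8. The CI of the sum excludes 0 in only about 5% of such trials. A test of the whole table is needed beside it.

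**Step 8: the direction of the inference.** With a true index of 0.20 and 25% Don't know, one arm's CI includes 0 with probability 0.66 at n = 40 and about 0.16 at n = 160. Under the rule, fewer respondents make a finding of successful blinding easier.

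**The case against.** **No trial-level verdict.** A reader might infer that a perfectly blinded trial would be reported as unblinded. The SAP does not support that. It states a result per arm and never combines them, and failing to reject unsuccessful blinding in an arm is not a declaration that blinding failed. This stands, and the point is limited to what the arm-level rule can distinguish.

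**The lean is assumed.** Nothing in the SAP shows that subjects would favour 'Active'. With little or no lean the rule mostly passes. Even then two separate 95% CIs give about 10% with at least one exclusion, so setting that beside 5% for a single contrast is not like for like. This also stands, which is why the range starts at d = 0 and shows both events.

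**The information is there.** Section 8.4.3.1 reports the answer counts and both indices, so a careful reader could see a shared lean. True, but the stated rule uses neither the signs nor the comparison.

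**Appendix 2 already covers negative values.** Only in part. It speaks of opposite guessing at an index of -1 with no don't-know answers, and gives no reading for moderate negative values.

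**The contrast alone is not enough.** Correct: Step 7 shows that it can be 0 when guesses do depend on the arm. It should be added to the per-arm indices and not replace them.

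**Low stakes.** Blinding is listed under other objectives, and the primary conclusion rests on the two-sample t-test. This limits the weight of the point but does not make the rule sound.

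**Conclusion.** The concern holds in this limited form. By the SAP's own estimator and rule, guesses independent of assignment with a shared lean d give indices of +d and -d, and the rule cannot separate them from +d and +d. This is algebra and rests on no assumption about the data.

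How often it would matter does rest on assumptions. It becomes the expected outcome in an arm once the lean reaches about 0.11 to 0.17. Below that it is a minority event in each arm, though at d = 0.10 at least one of the two arms is still affected in 53% of trials. At 0.15 the 84% counts at least one arm, while both arms are affected in 36%. Which count applies cannot be settled, because the SAP does not say whether one or both arms must pass.

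Two further inferences are not supported: that the SAP would declare the whole trial unblinded, and that the efficacy conclusion is at risk. The primary test does not depend on the blinding result.

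**What to change.** In Section 8.4.3.1 and Appendix 2:

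- Keep the per-arm Bang indices with 95% CIs and read them jointly with their signs. Positive in active and negative in sham indicates a shared lean towards 'Active', not unblinding. Positive in both indicates that guesses track assignment.
- Add the contrast BI_active + BI_sham with a 95% CI, taking the variance as the sum of the two Appendix 2 variances, at V3 and V6 separately.
- Add a test of independence on the full 2x3 guess-by-arm table at each of these visits, because differences in 'Don't know' cancel in the sum.
- Report all of these as estimates of how far guesses depend on the arm. Delete the sentence that rejects unsuccessful blinding when a CI includes 0, and the matching hypotheses in Appendix 2, since a CI that includes 0 does not demonstrate blinding.

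The cost is SAP wording and a few output lines from data already collected.

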#### **8.4.3.2 Subject satisfaction question**

The number and percentage of subjects reporting each choice will be reported by device group.

#### **8.4.3.3 Ease of use**

The number and percentage of subjects reporting each choice will be reported by device group.

#### **8.4.3.4 Subgroup Analyses**

The primary efficacy analysis and key secondary analyses will be repeated in subgroups of subjects based on the presence or absence of aura. The subgroup analyses will be performed in the ITT population. The analyses to be repeated are:

- Number of migraine days: comparison of treatment groups
- Responder rate as measured by percentage reduction in migraine days
- Number of headache days: comparison of treatment groups
- Number of days with acute headache medication: comparison of treatment groups

Analyses will be performed for each subgroup separately.

Additional subgroup analyses stratified by sex and/or stratified by race may also be performed.

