### **8.4 Efficacy Analyses**

#### **8.4.1 Primary Efficacy Analysis**

The primary efficacy analyses will be performed on the ITT population and will be repeated in the PP population, if the sample size between the two groups differ by more than 5%.

Summary statistics for the primary variable, change from 4-week run-in period, will be presented by treatment group. Missing data will be imputed per section 7.4.1.

The number of migraine days will be summarized descriptively for each study phase (run-in and DB) and by treatment group. The summary statistics for each visit, change between the double-blind and 4-week run-in period and percentage change between the double blind and 4-week run-in period (a secondary endpoint) will be summarized by mean, standard deviation, median, minimum, and maximum.

The two-sided, 95% confidence interval (CI) of the difference between the two device groups (active minus sham) in change from 4-week run-in period will be produced and the p-value will be calculated based on a two-sample t-test. If the p-value from the two-sample t-test is less than 0.05, then the null hypothesis will be rejected.

As sensitivity analyses, the two groups will be compared using analysis of covariance (ANCOVA) models with change from 4-week run-in period as the dependent variable and treatment group, and center as fixed effects with the number of migraine days in the 4-week run-in period as a covariate and again with treatment group, center, and aura as fixed effects with number of migraine days in the 4-week run-in period as a covariate. The adjusted means, adjusted mean difference and 95% confidence interval for the adjusted mean difference based on the ANCOVA models will be reported. The p-values tests that the adjusted mean difference between groups at Month 3 equals zero will be reported.

Further sensitivity analyses will investigate the robustness of the analysis to missing data (missing data refers to data points imputed in the calculations presented in section 7.4.1) by implementing multiple imputation and the pattern-mixture model (PMM) with control-based pattern imputation as summarized by Ratitch and O'Kelly (2011). This PMM sensitivity analysis addresses the possibility that the missing data is missing not at random (MNAR), meaning the missing data is not independent of the unobserved outcomes

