#### **8.4.3.6 Pooling Analyses**

Poolability of study sites will be assessed by comparing change in migraine days= trt\*site interaction; if  $p < 0.10$ , results will be stratified by site. Sites with less than five (5) subjects enrolled will be combined into a pseudo-site for purposes of analysis. To protect against having an overly large pseudo-site, when one

pseudo-site exceeds ten subjects, a second pseudo-site will be formed. This process will continue as needed each time a pseudo-site exceeds ten subjects.

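### The aura subgroups are analysed separately, and the SAP gives no estimate or test of whether the treatment effect differs by aura

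*SAP*

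**What the plan says.** SAP section 8.4.3.4 has the primary and key secondary analyses "repeated in subgroups of subjects based on the presence or absence of aura". It lists four outcomes: migraine days, responder rate, headache days and days with acute headache medication. It then adds: "Analyses will be performed for each subgroup separately". Further subgroups by sex and race are optional.

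The primary analysis to be repeated is the two-sample t-test of section 8.4.1, which carries a decision rule: "If the p-value from the two-sample t-test is less than 0.05, then the null hypothesis will be rejected". Section 8.4.2 attaches the same 0.05 rule to Fisher's exact test for responders. For headache days and medication days it gives summary statistics and 95% CIs, with no named test or decision rule.

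Elsewhere aura appears only as a main effect. The second sensitivity ANCOVA in section 8.4.1 is run "again with treatment group, center, and aura as fixed effects with number of migraine days in the 4-week run-in period as a covariate", and the second sensitivity logistic model in section 8.4.2 has the same structure. The only interaction in the SAP concerns sites (section 8.4.3.6): "Poolability of study sites will be assessed by comparing change in migraine days= trt\*site interaction".

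**The concern.** Whether the device works differently with and without aura is a question about the difference between two treatment effects. Two separate within-stratum analyses do not answer it, because one can be significant and the other not when the true effects are identical, particularly if the strata differ in size. The sensitivity models do not answer it either: with aura as a main effect only, they assume one common treatment effect (a common odds ratio in the logistic model).

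A reader of the results would therefore have two p-values per outcome for migraine days and responders, and no reported contrast between strata. What is at stake is a later statement that the device works only with, or only without, aura when the data do not support it.

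**Working it through.** **Inputs.** Section 3.5 sets the error rate and power ("Assuming a type I error of 5% (two-sided) and 90% power") and the planning case: "Selecting an improvement of 1 day and a common standard deviation of 2.5 requires 133 subjects per treatment group". It randomizes 160 per group after allowing for 15% drop-out. The SAP gives no aura prevalence, so a smaller-stratum share f of 20% to 50% is assumed here. It makes no difference to the figures whether the smaller stratum is with or without aura.

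**The plan's own figure.** n = 2(1.960 + 1.282)² × 2.5² / 1² = 131.4, so 132 per group, against 133 stated. The noncentral t gives 90.1% power at 133. Drop-out: 133/0.85 = 156.5, so 157, against 160 stated. The planning figures reproduce closely.

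**Power within a stratum.** With m per arm in a stratum, SE = 2.5√(2/m) and power ≈ Φ(1/SE − 1.960). Example, 133 per arm split 50:50: m = 66.5, SE = 0.434, 1/SE = 2.306, power = Φ(0.346) = 0.636.

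**Chance that exactly one stratum is significant.** The strata contain different subjects, so this is p₁(1 − p₂) + p₂(1 − p₁). In the example, 2 × 0.636 × 0.364 = 0.463.

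**Interaction.** The difference between the stratum effects has SE = 2.5√(2/m₁ + 2/m₂).

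| Per arm | Split | Power, smaller / larger stratum | Exactly one p<0.05 | Interaction SE (days) | Interaction power, 1-day difference |
|---|---|---|---|---|---|
| 133 | 20:80 | 0.308 / 0.831 | 0.627 | 0.766 | 0.257 |
| 133 | 30:70 | 0.431 / 0.779 | 0.538 | 0.669 | 0.321 |
| 133 | 50:50 | 0.636 / 0.636 | 0.463 | 0.613 | 0.371 |
| 160 | 20:80 | 0.359 / 0.893 | 0.610 | 0.699 | 0.299 |
| 160 | 30:70 | 0.500 / 0.849 | 0.500 | 0.610 | 0.374 |
| 160 | 50:50 | 0.716 / 0.716 | 0.407 | 0.559 | 0.432 |

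Under equal effects, the chance of exactly one significant stratum therefore runs from about 41% to 63%.

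**Simulation check** (40,000 trials per split, t-tests, 133 per arm, equal 1-day effects). Exactly one stratum was significant in 58% (25:75), 54% (30:70), 51% (35:65) and 47% (50:50). A two-sided 5% interaction test rejected in about 5.1% at each split. Among the discordant trials it rejected in only 7% to 10%, so most discordant pairs would be shown to be compatible with a common effect.

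**What the interaction test can detect.** At 133 per arm, 90% power needs a difference in effect of (1.960 + 1.282) × SE, which is 1.99 days at 50:50 and 2.48 days at 20:80.

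**The case against.** The strongest reply is that the SAP does nothing wrong on its face. It plans separate summaries under Other Efficacy Analyses, states no hypothesis about heterogeneity and sets no rule for claiming an aura-specific effect. A reader might infer that the plan intends to compare stratum p-values; the text does not say so. This stands, and the point is put here as a gap in what is reported, with a risk of misreading.

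The 41% to 63% and the 5% are also different kinds of quantity. The first is the chance of discordant p-values and the second is the error rate of a formal test. A reader might take the first as the plan's false-claim rate. It becomes one only if discordance is treated as proof of a difference. This stands too.

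The repeated primary analysis already yields a difference and 95% CI in each stratum, from which an approximate CI for the contrast can be derived. That is true for migraine days. It leaves the reader to do the calculation, and the plan neither asks for it nor cautions against comparing p-values.

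Finally, a 0.05 decision rule exists for only two of the four outcomes, and an interaction test here is weak. Both are correct and shape the fix. Neither supplies the missing estimate.

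**Conclusion.** The point holds as a minor one about interpretation. The SAP specifies separate aura-stratum analyses and nowhere estimates or tests the difference between them, although it uses an interaction test for sites. With equal true effects of 1 day, exactly one stratum would be significant in about 41% to 63% of trials. This rests on SD 2.5, 133 to 160 per arm with the full effect retained, and an assumed aura share of 20% to 50%. The exact figure moves with the split, but it is at least about 41% at every split tried.

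It might be inferred that the trial's main conclusion or its type I error is compromised. It is not: the primary test uses the whole ITT population and does not depend on the subgroup results.

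**What to change.** - Add a treatment-by-aura term to the aura ANCOVA for migraine days and to the aura logistic model for responders.
- Fit the same ANCOVA with interaction for headache days and acute-medication days, for which the SAP now specifies no model.
- For each outcome, report the interaction estimate with 95% CI and p-value, and the stratum effects with CIs. In the logistic model the interaction is a ratio of odds ratios and should be labelled as such.
- State that stratum p-values for migraine days and responders are not decision rules.
- Apply the same approach to any sex or race subgroups.

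The cost is one term in two planned models and two additional ANCOVAs, with no new data and no change to the primary test or sample size. The small downside is low power. The interaction SE is about 0.56 to 0.77 days over 133 to 160 per arm, and power for a 1-day difference in effect is about 26% to 37% at 133 per arm. The SAP should therefore say that a non-significant interaction is not evidence of equal effects and that the CI is the main result.
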